Protocol Synopsis

Name of Sponsor: Korea Otsuka Pharmaceutical Co., Ltd.	Protocol#
Name of Investigational Medicinal Product: Cilostazol (Pletaal® SR cap.)	021-KOA-1201n
Protocol Title:	A Prospective, Post Marketing Observational Study to evaluate the safety of Pletaal® SR capsule
Clinical Phase:	Post Marketing Observational Study
Treatment Indication:	1. Treatment of ischemic symptoms including ulceration, pain and coldness in chronic arterial occlusion (Berger's disease, arteriosclerosis obliterans, diabetic peripheral angiopathy). 2. Prevention of recurrence of cerebral infarction (excluding cardiogenic cerebral embolism).
Objective(s):	
Pletaal® SR capsule(q.d.) is developed and approved as improving Pletaal® Tablet(b.i.d.). But there is no safety data of Pletaal® SR capsule. The objective of this study is to evaluate following items in relation with use of Pletaal® SR capsule in general medical practice;
 
1. Serious adverse event and adverse drug reaction profile2. Unexpected adverse event/adverse drug reaction profile3. Known adverse drug reaction profile4. Adverse event of product abuse/misuse, drug interactions or overdose5. Other information related to the product safety 
The hypothesis of this study is that Pletaal® SR capsule is safe in the treatment.

Trial Design & Method:	This is a Post Marketing Observational Study of cilostazol (Pletaal® SR capsule). This study will be conducted in a prospective, single-arm, multi-center format. As this study is observational in nature to collect the safety data after administrating the Pletaal SR capsule, from baseline to 16 weeks. The patient's follow-up is not prescriptive in nature and must be left up to the judgment of the physician (investigator), within the period of observation set forth in the protocol.
Trial Population:	At least 3000 patients will be enrolled for this study to collect the safety data among various groups. Investigators across the country will be participating in this study and the number of patients to be enrolled by each investigator will vary.


Inclusion/Exclusion Criteria:
	
Inclusion Criteria
 
Patients must meet all of the following inclusion criteria to be eligible for enrollment into the study :
 
 1. Patients who are prescribed Pletaal® SR capsule treatment as per investigator's medical judgment for adults aged 19 and over. 2. Patients who gave written authorization to use their personal and health data 
Physician (Investigator) will refer to the product market authorization (package insert) for inclusion criteria.
 
Exclusion Criteria
 
Patients presenting with any of the following will not be included in the study
 
 1. Patients with hemorrhage 2. Patients with congestive heart failure 3. Patients with known hypersensitivity to Cilostazole or any ingredients of Pletaal® 4. Women who are pregnant or may possibly become pregnant 5. Patients who is not eligible to participate this study as investigator's medical judgment 
Physician (Investigator) will refer to the product market authorization (package insert) for exclusion criteria.

Investigational Medicinal Product(s), Dose, Dosage regimen, Treatment period, Formulation, Mode of Administration:
	
The usual adult dose of Pletaal® SR capsule is 200mg of cilostazol, once daily, by the oral route. This is taken in the fasting state, avoid eating.

Safety Measure:	
1. The incidence rate and the number of AE/ADRs2. The incidence rate of Tarchycardia and Palpitation after Pletaal® SR capsule administration3. The number and percentage of drop-out patients according to AEs4. The difference between AE and drug compliance according to patient's character
-----------------	---

Statistical Methods:	1. Demographic Information & Baseline Characteristics
	Data for the baseline characteristics is demonstrated by descriptive statistics. Mean, standard deviation(SD), minimum value, median, maximum value for continuous variables and frequency(n), percentage(%) for categorical variables will be presented in overall patients.
	2. Safety Analysis
	
 - The incidence rate and the number of AE/ADRs - The incidence rate of Tachycardia and Palpitation after Pletaal® SR capsule administration - The number and percentage of drop-out patients according to AEs - The difference between AE and drug compliance according to patient's character
	
All adverse events (AEs) observed during/after the administration will be analyzed as safety assessment. The number of patients and the number of AE/ADR, SAE/Serious ADR (SADR), unexpected AE/ADR will be calculated (frequency and percentage). In the final report, the incidence rate of all AEs during the study period will be estimated with its 95% confidence interval.

	
The number and percentage of drop-out patients according to AEs and the incidence rate of AEs for the severity will be estimated. Safety measures will be summarized and analyzed to find the risk factors in overall patients by background factors (baseline characteristic, drug administration, concomitant drug treatment etc.). The analysis will be performed using Chi-square test or Fisher's exact test.

	
The number and percentage of AEs/ADRs will be summarized for special population (elderly patients, patients with liver or renal disease).

	
Record the term of adverse event according to the System Organ Class, Preferred Term, Lower-Level Terms in the Medical Dictionary for Regulatory Activities (MedDRA). If there is no preferred term, look up the WHO Adverse Reactions Terminology (WHOART).

Estimated Duration of study	
Planned study schedule is as below;
 
1. Study duration: Jan 2013 – Dec 20142. Submit the final reports to KFDA: within 1 year of study completion3. Submit the CSR to global within one year after LPLV or end of data collection as defined in protocol or contract
-----------------------------	--

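### Does leaving prior cilostazol use and the first SR dose unspecified make the pooled adverse event incidences misleading?

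*Protocol*

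**What the plan says.** Inclusion criterion 1 admits "Patients who are prescribed Pletaal® SR capsule treatment as per investigator's medical judgment for adults aged 19 and over". None of the listed criteria asks for a first SR prescription or for no earlier cilostazol. None excludes tablet users or patients already on the capsule.

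Trial Design & Method describes a prospective single-arm study "to collect the safety data after administrating the Pletaal SR capsule, from baseline to 16 weeks". The Objective(s) section notes that the capsule "is developed and approved as improving Pletaal® Tablet(b.i.d".), so an older form of the same substance exists from which patients may switch. The same section sets the aim as describing the safety of the capsule in ordinary medical practice.

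Under Statistical Methods, Safety Analysis, "the incidence rate of all AEs during the study period will be estimated with its 95% confidence interval". A listed safety measure is "The incidence rate of Tachycardia and Palpitation after Pletaal® SR capsule administration". The safety measures are also to be examined for risk factors "by background factors (baseline characteristic, drug administration, concomitant drug treatment etc".). Prior cilostazol use is not named there, nor among the special populations (elderly patients and those with liver or renal disease).

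**The concern.** A cohort that mixes people starting a drug with people who already tolerate it can give too favourable a picture of starting it. Early events in patients already on the capsule would fall before baseline, and those who stopped early would never be enrolled. Patients switched from the tablet have already shown that they tolerate the substance.

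Tachycardia and palpitation are singled out as safety measures, and the protocol justifies the study by the absence of safety data on the SR form. A reader might therefore take the pooled incidence as the risk a new patient faces. A sample of 3000 narrows the confidence interval but does not remove a shift of this kind. If neither prior use nor the first-dose date were collected, no later analysis could separate the groups.

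**Working it through.** **The plan's own figure.** The only number fixed is the minimum enrolment of 3000. No rate, precision or power is given for it, so there is nothing to reproduce, and the number is not in dispute here.

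**Size of a possible gap.** Let p0 be the risk in new users, s the share of prior users, and RR the risk in prior users relative to new users. All three are assumptions; the protocol gives none of them.

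- Pooled risk = p0 × [(1 − s) + s × RR]
- Relative understatement = s × (1 − RR)
- 95% interval = p ± 1.96 × √(p(1 − p)/3000)

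Worked example: p0 = 3%, s = 30%, RR = 0.5. Pooled = 3% × (0.7 + 0.15) = 2.55%. Half-width = 1.96 × √(0.0255 × 0.9745/3000) = 0.56 points, so the interval is 1.99% to 3.11% and covers 3%.

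| p0 | RR | s | Pooled (95% interval) | Covers p0? |
|---|---|---|---|---|
| 3% | 0.5 | 10% | 2.85% (2.25–3.45) | yes |
| 3% | 0.5 | 30% | 2.55% (1.99–3.11) | yes |
| 3% | 0.5 | 50% | 2.25% (1.72–2.78) | no |
| 3% | 0.8 | 50% | 2.70% (2.12–3.28) | yes |
| 10% | 0.5 | 10% | 9.5% (8.45–10.55) | yes |
| 10% | 0.5 | 30% | 8.5% (7.50–9.50) | no |
| 10% | 0.5 | 50% | 7.5% (6.56–8.44) | no |
| 10% | 0.8 | 50% | 9.0% (7.98–10.02) | yes, narrowly |

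At RR = 0.8 smaller values of s move the pooled figure less, so those intervals cover p0 as well. With s = 0 or RR = 1 there is no gap. With RR = 1.5, as might happen if patients were switched because they tolerated the tablet poorly, the pooled figure is too high by 5%, 15% and 25% at s = 10%, 30% and 50%. At a harsh extreme, s = 70% and RR = 0.25, the pooled figure is 1 − 0.7 × 0.75 = 47.5% of new-user risk. The assumptions alone thus decide both the sign and the size.

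**What the text already settles.**

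1. *Start of the window.* Trial Design & Method places data collection after SR administration, from baseline, in a prospective study, and the tachycardia and palpitation measure is also worded as following administration. The ordinary reading is that the 16 weeks begin with SR treatment. No statement puts baseline in mid-treatment.
2. *Background factors.* Prior use fits under baseline characteristics or drug administration, and the list is left open.
3. *Target.* The protocol sets out to describe safety among patients prescribed the capsule in practice. New-user risk appears neither as an objective nor as a safety measure. For the stated target, the pooled incidence is the right summary.

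**Two groups, not one.** Fixing baseline at the first SR dose concerns only patients already on the capsule. A patient switched from the tablet has earlier cilostazol exposure wherever baseline is set, and belongs to the population that the objective describes.

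**The case for a change.** The strongest opposing case is that eligibility and the start of observation are design matters. A statistical analysis plan can add a table by prior use only if prior use and the first-dose date are on the case report form. If they are not, the question cannot be answered afterwards. The protocol itself points to an existing tablet, so prior users are a real possibility. Recording the items would be cheap, and the price of splitting the results is modest: at an assumed 3% risk and 30% prior users, half-widths of 0.73 points (n = 2100) and 1.11 points (n = 900), against 0.61 points for all 3000.

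Part of this stands. The protocol does not say in so many words that baseline is the first SR dose, and it does not name prior cilostazol use. A larger sample would not cure a shift if one existed.

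The argument nevertheless depends on the data not being collected, and nothing in the protocol shows that. The text is a synopsis, and it refers to the protocol for the observation period. What is recorded at baseline belongs to the case report form, and which subgroups are tabulated belongs to the analysis plan; neither was available for this review. Cheapness does not make an unwritten detail an error.

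**Conclusion.** No change to the plan is called for. Followed as written, it gives a sound pooled incidence for the patients it sets out to describe. What remains is an unstated definition and an unnamed factor, a gap that analysts can be expected to fill sensibly within the open list of background factors.

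No bias has been demonstrated. Over assumed shares of 10% to 50%, the pooled figure would be 2% to 10% below new-user risk at RR = 0.8 and 5% to 25% below at RR = 0.5. It would equal new-user risk at RR = 1 and lie 5% to 25% above it at RR = 1.5. For the 3% and 10% risks tried, the shift stays within sampling error in every case at RR = 0.8 and in three of six cases at RR = 0.5.

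The caution that survives concerns interpretation: the pooled incidences describe the enrolled mix of users and should not be quoted as the risk on first starting cilostazol. This conclusion rests on reading the 16-week window as beginning with SR treatment. It would weaken if the case report form turned out to record neither prior use nor the first-dose date.

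### The risk-factor tests ignore observation time although follow-up may vary within 16 weeks; a Kaplan-Meier estimate and log-rank test beside the crude results would be a cheap safeguard

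*Protocol*

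**What the plan says.** Under Trial Design & Method, the study is "to collect the safety data after administrating the Pletaal SR capsule, from baseline to 16 weeks". The same paragraph says that follow-up "must be left up to the judgment of the physician (investigator), within the period of observation set forth in the protocol". Trial Population gives the size: "At least 3000 patients will be enrolled for this study to collect the safety data among various groups".

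Under Statistical Methods, 2. Safety Analysis, three statements bear on time:

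- The counts of patients and of events "will be calculated (frequency and percentage").
- The main estimate: "In the final report, the incidence rate of all AEs during the study period will be estimated with its 95% confidence interval". Safety Measure lists the same quantity as "The incidence rate and the number of AE/ADRs". Neither place says whether the denominator is patients or person-time.
- The search for risk factors is made "by background factors (baseline characteristic, drug administration, concomitant drug treatment etc".), and its method is fixed: "The analysis will be performed using Chi-square test or Fisher's exact test".

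The protocol also plans to tabulate drop-outs due to AEs. It gives no expected AE risk and no expected rate of early leaving.

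**The concern.** The sentence on Chi-square and Fisher's exact tests is the firm ground. It names a method that compares proportions and takes no account of how long each patient was observed, in a design where that length is left open. If two background-factor groups have the same AE hazard but one is observed longer, it accumulates more AEs, and the test can report an association that reflects observation time only.

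Two of the named factors, drug administration and concomitant treatment, carry an extra risk if they are recorded over follow-up. A patient watched longer has more chance both to start a second drug and to have an AE recorded. The protocol does not say whether these factors are taken at baseline.

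The overall estimate is a weaker anchor, because its denominator is undefined. If it is the crude percentage, it describes AEs seen during whatever time each patient was watched. That is a legitimate description, but not the 16-week risk if patients leave early.

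These are the main quantitative safety results of a single-arm study, so a reader should be able to tell risk from observation time.

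**Working it through.** The protocol states no derived figure to reproduce. What follows is an illustration. Only the first two inputs come from the document.

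**Inputs**
- N = 3000 (Trial Population, a minimum).
- Window T = 16 weeks (Trial Design & Method).
- Assumed: true 16-week risk of a first AE, R = 10%.
- Assumed: a share f leaves uniformly over 0 to 16 weeks for reasons unrelated to AEs.
- Assumed AE timing, two cases: (A) constant hazard; (B) early AEs, with 8% cumulative risk by week 4 and 10% by week 16, the hazard constant within each piece.

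**Step 1. Mean risk observed in an early leaver**
- A: H = -ln(0.9) = 0.10536; 1 - (1 - 0.9)/0.10536 = 5.09%.
- B: mean survival is (0.92's complement 0.08)/0.08338 = 0.9594 over weeks 0-4 and 0.02/0.02198 = 0.9100 over weeks 4-16; 1 - (4 × 0.9594 + 12 × 0.9100)/16 = 7.77%.

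**Step 2. Crude percentage** = (1 - f) × 10% + f × (Step 1 risk)

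| f | A: crude | B: crude |
|---|---|---|
| 0% | 10.0% | 10.0% |
| 5% | 9.75% | 9.89% |
| 10% | 9.51% | 9.78% |
| 20% | 9.02% | 9.55% |
| 30% | 8.53% | 9.33% |

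The half-width of the 95% interval is 1.96 × sqrt(0.1 × 0.9/3000) = 1.07 points. The shortfall equals it at f = 1.07/4.91 = 22% (A) or 1.07/2.23 = 48% (B). Exact binomial coverage of the true 16-week risk by the Wald interval is 92% (A) or 94% (B) at f = 5%, and 52% or 85% at f = 20%.

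**Step 3. Risk-factor test with equal hazard and 10% versus 30% leaving**

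The crude proportions are 9.51% and 8.53% (A), or 9.78% and 9.33% (B). With difference d, pooled standard error s0 and unpooled standard error s1, the rejection probability is Φ((d - 1.96 s0)/s1) + Φ((-d - 1.96 s0)/s1).

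For A with 1500 per group: d = 0.00982, s0 and s1 both about 0.01046, giving Φ(-1.02) + Φ(-2.90) = 15.6%.

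| Group sizes | A | B |
|---|---|---|
| 1500 and 1500 | 15.6% | 7.0% |
| 2700 and 300, smaller group leaves more | 7.6% | 5.3% |
| 2700 and 300, smaller group leaves less | 9.9% | 6.1% |

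At 10% versus 20% leaving with 1500 per group the figures are 7.5% and 5.5%.

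**Step 4. A factor recorded during follow-up**

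Suppose 30% of patients would start a concomitant drug at a uniform time, unrelated to AEs, and f = 20%. Under A:
- Recorded starters are 0.8 × 0.3 = 0.24 of patients with full follow-up, plus 0.2 × 0.3 × 0.5 = 0.03 who leave after starting. These leavers were watched longer than average; their mean risk is 1 - 2(1 - 0.9 × 1.10536)/0.10536² = 6.75%. Crude risk: (0.24 × 10% + 0.03 × 6.75%)/0.27 = 9.6%.
- Non-starters: 0.56 with full follow-up, 0.14 ordinary leavers at 5.09%, and 0.03 who left before starting, at 2 × 5.09% - 6.75% = 3.4%. Crude risk: (0.56 × 10% + 0.14 × 5.09% + 0.03 × 3.4%)/0.73 = 8.8%.

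Simulation gives the same percentages, with Chi-square rejection of about 11%. Under B it gives 9.9% versus 9.4% and about 7%.

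**Step 5. Time-aware methods on the same assumptions (simulated)**

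Kaplan-Meier averages 10.0%, with coverage of 94.5% to 95.9%. At 10% versus 30% leaving the log-rank test rejects 5.5% (A) or 4.7% (B). A rate-ratio test rejects 4.8% (A) but 9.0% (B), no better than the 7.0% of Chi-square.

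**The case against.** The strongest objection is that this asks for an addition. Denominators, censoring rules and supplementary estimators usually sit in a statistical analysis plan, which is not shown. That stands for the overall estimate: the lack of a time-aware figure here is not an error. It does not dispose of the risk-factor sentence, where the protocol itself chooses the method.

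Three stronger readings are tempting, and the document does not support them.

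- *That observation is unequal.* Leaving follow-up to the physician inside a common 16-week period may mean only that visits are not mandated. The text permits unequal observation but does not establish it.
- *That the planned incidence rate is a crude percentage and therefore biased.* The wording is compatible with a person-time rate. The neighbouring frequency and percentage make a crude proportion the more natural reading, no more than that.
- *That the planned tabulation of AE-related drop-outs shows the bias.* A patient who stops because of an AE is already counted among patients with an AE, so this does not lower the any-AE percentage. The shortfall needs leaving unrelated to AEs, on which the protocol is silent.

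It is also fair that an equal split shows the false-rejection problem near its largest, that early AEs shrink every effect, and that the risk-factor search is exploratory. These points limit the size of the concern but do not remove it.

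**Conclusion.** A worthwhile, low-cost improvement, not an error in the plan. What holds is that the Chi-square and Fisher's exact tests fixed in Safety Analysis do not use observation time, the design allows that time to differ, and the incidence rate has no stated denominator.

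The actual size cannot be known from the document. On the assumed 10% risk, the effect runs from nothing with complete follow-up to a shortfall of 0.4 to 1.0 points at 20% leaving, nearly the full interval half-width in the worse case. False rejection is about 5% to 16% at 10% versus 30% leaving, depending on AE timing and group split. All of this assumes uniform leaving unrelated to AEs. With 5% leaving the shortfall is only 0.11 to 0.25 points.

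**What to change.** Keep the crude table, with its percentage defined as patients with an AE over treated patients, and keep the Chi-square or Fisher's exact tests. Then:

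- Report the distribution of observation time, overall and by background factor.
- Add the Kaplan-Meier 16-week cumulative incidence of first AE/ADR with its 95% confidence interval.
- Add a log-rank test for background factors known at baseline. It is preferable to a rate ratio, which fails when AEs come early.
- Define a factor that can change during follow-up, such as a concomitant drug, by its baseline status, or handle it as time-dependent.

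The cost is a few sentences and a little programming, with no extra patients or visits. End-of-observation and AE-onset dates are needed for every patient, and the document does not show whether the case report form holds them.

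The added estimate assumes independent censoring. In simulation with 20% leaving, if leavers have twice the hazard the true risk is 11.8%, Kaplan-Meier gives 11.0% and the crude figure 10.0%. If they have half the hazard, the true risk is 9.0%, Kaplan-Meier gives 9.5% and the crude figure 8.5%. Kaplan-Meier is nearer in some detail, but not unbiased, so reasons for leaving should be reported beside it.

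### The search for AE risk factors relies on one-factor-at-a-time chi-square or Fisher tests, with no adjustment and no label saying so

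*Protocol*

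**What the plan says.** Under Statistical Methods, 2. Safety Analysis, the protocol states a purpose: "Safety measures will be summarized and analyzed to find the risk factors in overall patients by background factors". The factors form an open list: "baseline characteristic, drug administration, concomitant drug treatment etc". The next sentence fixes the method: "The analysis will be performed using Chi-square test or Fisher's exact test".

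The related item 4 under Safety Measure is worded as a comparison only: "The difference between AE and drug compliance according to patient's character".

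The design is given under Trial Design & Method: "This study will be conducted in a prospective, single-arm, multi-center format". The size is given under Trial Population: "At least 3000 patients will be enrolled for this study to collect the safety data among various groups".

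The protocol names no multivariable model or stratified test, and it does not call these comparisons unadjusted, univariable or exploratory. The statistical analysis plan was not available for this review.

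**The concern.** A chi-square or Fisher test on a two-way table validly shows whether AE risk differs between groups. That is enough for item 4 under Safety Measure. It cannot show whether the tabulated factor or a correlated one accounts for the difference. The Safety Analysis text goes further than item 4 because it aims to find risk factors.

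No background factor is randomised. Elderly patients and patients with liver or renal disease, whom the protocol itself singles out for separate summaries, may overlap, and concomitant treatment may go with either. A real group difference could therefore be reported as a risk factor when a correlated factor explains it. The final report goes to the regulator, and the Objective(s) section says there are no safety data yet for this formulation, so such a list could be misread.

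Only the risk-factor search is at stake. It is not one of the five numbered objectives.

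**Working it through.** The protocol gives no significance level, power or effect size for this analysis, so there is no figure of its own to reproduce. What follows illustrates the mechanism.

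**Inputs.** From the protocol: at least 3000 patients, one arm, chi-square or Fisher's exact test. Assumed: two-sided 5% level; 1500 older and 1500 younger patients; AE risk without renal disease p0 = 7%; renal-disease risk ratio RR of 1.5, 2.0 or 2.5; renal prevalence 10% in younger patients and 15%, 20%, 25% or 40% in older ones; no age effect given renal disease.

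**Step 1: AE risk by age group.** Risk = p0 × [1 + prevalence × (RR − 1)]. For 40% against 10% and RR = 2.0:
- older: 0.07 × (1 + 0.40) = 9.80%
- younger: 0.07 × (1 + 0.10) = 7.70%

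This difference is real but is due entirely to renal disease.

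**Step 2: chance that the unadjusted test is significant.** Two-proportion power with pooled variance under the null is approximately Φ[(d − 1.96 × SE0) / SE1], where d is the risk difference and SE0 and SE1 are its standard errors under the null and the alternative. In the example:
- d = 0.021 and the pooled risk is 0.0875
- SE0 = √(2 × 0.0875 × 0.9125 / 1500) = 0.01032
- SE1 = √[(0.098 × 0.902 + 0.077 × 0.923) / 1500] = 0.01031
- (0.021 − 1.96 × 0.01032) / 0.01031 ≈ 0.075, and Φ(0.075) ≈ 0.53

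All twelve scenarios at p0 = 7%:

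| Renal prevalence, older vs younger | RR 1.5 | RR 2.0 | RR 2.5 |
|---|---|---|---|
| 15% vs 10% | 5.4% | 6.5% | 8.2% |
| 20% vs 10% | 6.5% | 10.9% | 17.7% |
| 25% vs 10% | 8.4% | 18.2% | 33.0% |
| 40% vs 10% | 18.7% | 53.0% | 83.3% |

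These are not false-positive rates. They are the chances of detecting a marginal age difference that renal disease explains.

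**Step 3: other assumptions.** Range over the same twelve scenarios:
- p0 = 1%: 5.1% to 18.5%
- p0 = 3%: 5.2% to 46.0%
- p0 = 15%: 5.9% to 99.6%
- p0 = 7% with 900 older and 2100 younger patients: 5.4% to 77.6%

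**Step 4: the same data with adjustment.** Simulation at p0 = 7% with 1500 per group and 20,000 studies per scenario, using a logistic model of AE on age group and renal disease. The Wald test for age was significant in 4.8% to 5.2% of studies. The median odds ratio (OR) for age was 1.03 to 1.44 crude and 1.00 adjusted.

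**Step 5: a second set-up.** Here 3000 patients have a true cause present in 30%. AE risk without it is 5%, 10% or 20%, and its risk ratio is 1.5, 2 or 3. A no-effect factor is present in 40% of patients with the cause and 25% without it, or in 60% and 20%. The unadjusted test flagged that factor in 6% to 100% of studies. A Mantel-Haenszel test stratified by the true cause flagged it in about 4-6%.

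**Step 6: events available for a model.** Expected patients with an AE = 1500 × (sum of the two group risks). At p0 = 7% this is 223 to 289, or 11 to 14 model terms at an assumed 20 events per term (223/20 and 289/20). At p0 = 1% it is 32 to 41, or 1 to 2 terms.

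**The case against.** The strongest reply is that nothing is misstated. The protocol never calls its risk factors independent or causal, and a characteristic marginally associated with AEs can fairly be called a risk marker. For describing which patients have more AEs, the marginal comparison is the relevant one. A two-way test is also unadjusted on its face, the design is openly observational, and the analysis plan may add a model.

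The numbers are open to challenge too. Every input is assumed, and detection is 20% or less in 37 of the 48 combinations with equal age groups (12 + 10 + 9 + 6 of 12 each, at 1%, 3%, 7% and 15% base risk). At 7%, it exceeds 50% only at 40% against 10% prevalence with RR of at least 2. If renal disease lies on the pathway from age to AEs, the crude OR is age's total effect and the adjusted 1.00 would hide it. For rare events the model is hardly usable.

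Much of this stands. It limits the grade to minor and argues for showing crude and adjusted results together. It does not remove the point: the protocol names both the aim and the test, so this is a stated method that serves its aim only in part. A reader of the final report should be told that the listed factors are unadjusted associations.

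**Conclusion.** The concern holds, as a minor point. The named tests support statements about group differences but not about which factor accounts for them, and the protocol neither adjusts nor says that it does not.

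The consequence is negligible if background factors are weakly correlated and large if a strong cause is much commoner in one group. Where this study falls between those ends cannot be known from the protocol, because AE risk, prevalences and risk ratios are not given. AE incidence with its 95% confidence interval and the descriptive tables do not depend on this choice.

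**What to change.** Keep the chi-square and Fisher tables and label them unadjusted and exploratory. For any AE and any adverse drug reaction, and for tachycardia and palpitation if events allow, add an exploratory multivariable logistic model on a pre-listed set of baseline factors. Report crude and adjusted ORs side by side with 95% confidence intervals. State that adjustment covers recorded factors only, and that an adjusted OR can understate a factor's total effect when another modelled factor lies on its pathway. Model details can sit in the analysis plan.

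The cost is one or two sentences and a little programming, using background factors already planned for analysis. The downside is that fewer factors will probably be reported as significant, and rare outcomes will support few model terms. Where events are too few for a model, the label alone corrects the text.

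### The risk-factor search names only chi-square or Fisher's exact tests, so continuous factors such as age are banded, their order is ignored, and power is lost for weak-to-moderate gradients

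*Protocol*

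**What the plan says.** In the Protocol Synopsis, Statistical Methods, 2. Safety Analysis, the safety measures are to be "analyzed to find the risk factors in overall patients by background factors (baseline characteristic, drug administration, concomitant drug treatment etc".) The method follows directly: "The analysis will be performed using Chi-square test or Fisher's exact test". Ordered or continuous factors get no separate treatment, and no bands are defined.

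Under 1. Demographic Information & Baseline Characteristics, the plan lists "Mean, standard deviation(SD), minimum value, median, maximum value for continuous variables", so some baseline characteristics, and hence some background factors, are continuous. Age is the obvious one: eligibility is "for adults aged 19 and over", with no upper limit.

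On size and design: "At least 3000 patients will be enrolled for this study to collect the safety data among various groups", and "This study will be conducted in a prospective, single-arm, multi-center format". The protocol attaches no event rate, effect size, significance level or power to the 3000, or to the factor tests.

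**The concern.** Chi-square and Fisher's exact tests compare categories, and in their usual form neither uses the order of the categories. A continuous factor must therefore be cut first. A two-way cut discards most of the within-group information. A finer cut keeps more of it, but spreads the test over several degrees of freedom and so dilutes it against the alternative that is most plausible for age: risk that rises or falls steadily.

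Finding risk factors is a stated purpose of this analysis, and the synopsis says that no safety data exist for the SR capsule. Missing a real gradient for lack of an efficient test on data already collected is an avoidable loss.

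**Working it through.** The protocol's 3000 cannot be reproduced because no basis is given for it; it is used here only as N.

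**Inputs**
- From the protocol: N = 3000 (the stated minimum), single arm; chi-square or Fisher's exact test for all background factors.
- Assumed: two-sided 5% level; AE incidence 10% or 5%; a normally distributed factor with log-linear risk and odds ratio (OR) 1.20 or 1.30 per SD; equal-sized bands; no dropout.

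**Formulas** (p̄ = overall risk, p_k = risk in band k, w_k = share of patients in band k, s_k = band score, x = the factor in SD units)
- Chi-square on K bands, K−1 df: λ = N Σ w_k(p_k − p̄)² / [p̄(1 − p̄)]
- Trend test, 1 df: λ = N [Σ w_k(s_k − s̄)p_k]² / [Var(s) p̄(1 − p̄)]
- Factor on its own scale (logistic score test), 1 df: λ = N Cov(x, p)² / [Var(x) p̄(1 − p̄)]
- Power = P(noncentral χ² with noncentrality λ exceeds the 95% point of χ²), which is 3.84 on 1 df and 9.49 on 4 df.

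**Worked case: 10% incidence, OR 1.20 per SD.** The five band risks are 7.85%, 9.05%, 9.88%, 10.78% and 12.43%.
- Five-band chi-square: the squared deviations average about 2.41 × 10⁻⁴. λ = 3000 × 2.41 × 10⁻⁴ / 0.09 ≈ 8.0 on 4 df; power 61%.
- Trend on the same bands, scores −2 to 2, Var(s) = 2: (−15.70 − 9.05 + 10.78 + 24.86)/5 = 2.18 points. λ = 3000 × 0.0218² / (2 × 0.09) ≈ 7.9 on 1 df; power 80%.
- Continuous: Cov(x, p) = 0.01636. λ = 3000 × 0.01636² / 0.09 ≈ 8.9 on 1 df; power 85%.
- Median split: risks 8.70% and 11.30%. λ = 3000 × 0.0130² / 0.09 ≈ 5.6 on 1 df; power 66%.

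Five bands keep about 90% of the continuous signal (8.0/8.9), so nearly all of that loss comes from the extra degrees of freedom. The median split keeps only about 63% (5.6/8.9).

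**Power at N = 3000: calculated (simulated)**

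| Incidence, OR per SD | Five-band chi-square | Median split | Five-band trend | Continuous |
|---|---|---|---|---|
| 10%, 1.20 | 61% (60%) | 66% (65%) | 80% (80%) | 85% (85%) |
| 5%, 1.20 | 34% (33%) | 41% (41%) | 53% (53%) | 58% (59%) |
| 10%, 1.30 | 92% (92%) | 93% (93%) | 98% (98%) | 99% (99%) |

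The two methods agree to about a point. Under no effect, all tests rejected in about 5% of simulated trials.

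**Limits of the loss**
- At 10% incidence and OR 1.5 per SD, every method has about 100% power.
- At 10% incidence and OR 1.1 per SD, every method usually misses: 19% (five-band chi-square), 31% (trend), 35% (continuous).
- For a two-level factor, the ordinary chi-square and the trend test are the same test, so nothing is lost.

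**Where chi-square is better.** Take quartiles at 10% incidence with the outer two at 1.5 times the risk of the inner two (12%, 8%, 8%, 12%). Chi-square: λ = 3000 × 0.02² / 0.09 = 13.3 on 3 df; power 88%. The trend test has 5%, its type I error.

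**The case against.** The strongest reply is that this is a synopsis, that bands and models belong in a statistical analysis plan, and that naming a family of tests does not exclude supplementary ones. Describing age by its mean and also tabulating AE rates by age group is no contradiction. The named tests are valid, the search is exploratory, and the term chi-square test could be stretched to cover a chi-square test for trend.

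Much of this stands, and it sets the weight of the point. The absence of band definitions is not itself a finding. What remains is that the protocol does not leave the method open: it names two tests for all background factors, and in their usual form these suit graded factors poorly. The text does not mention trend.

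Several stronger readings are tempting but unsupported:
- That cut-points will be picked after seeing the data. The protocol is silent on bands and says nothing of the kind.
- That dose gradients will be missed. The synopsis gives one usual dose ("The usual adult dose of Pletaal® SR capsule is 200mg of cilostazol, once daily, by the oral route"), so little dose gradient is to be expected; age is the better example.
- That the method falls short of the power for which 3000 patients were chosen. The protocol claims no such basis.
- That AE severity is a graded risk factor handled badly here. In the synopsis, severity describes the event, which is the outcome.
- That chi-square should give way to a trend test. The U-shaped case above shows what that would lose.

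**Conclusion.** The point holds as a minor one about efficiency. The named tests neither inflate type I error nor bias the AE incidence estimate and its confidence interval. They cost roughly 15 to 25 points of power for a monotone gradient of OR 1.20 per SD at 5% or 10% incidence. The loss is about 6 to 7 points at 10% incidence and OR 1.3, and negligible for strong gradients with common events. At a given gradient it can remain substantial for less common events: at 5% incidence and OR 1.3, calculated power is 65% (five-band chi-square), 83% (trend) and 88% (continuous).

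The direction of the loss holds for any roughly monotone relation in a continuous factor or one with three or more ordered levels. Its size rests on the assumed incidence, gradient, bands and 5% level, none of which the protocol gives.

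**What to change.** Replace the test sentence in 2. Safety Analysis with wording such as:

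> Nominal and two-level factors are compared by chi-square or Fisher's exact test. For ordered factors, a Cochran-Armitage trend test is reported in addition to the ordinary chi-square test. For continuous factors such as age, a logistic model for the patient-level event is also fitted, with the factor on its own scale and a check for curvature. Banded tables use cut-points fixed before database lock. All of these analyses are exploratory.

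Keeping the ordinary chi-square beside the trend test protects against non-monotone patterns in ordered factors; the curvature check does so for continuous ones. The cost is a wording change and a few lines of standard code, with no new data or patients. The downside is a little more analysis work and a few more tests, which is why the exploratory label is needed.
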